2.2 BACKGROUND

In collaboration with a media services company (Triad Interactive Media, Greensboro, NC), we developed a radon app for smartphones.¹¹ Briefly, the app uses a framework in HTML5 and the open source Twitter API. Posts created by the app are cross-listed on Twitter. Once users log in via Twitter, they can view radon news and mobile-friendly informative content on radon repurposed from EPA brochures. Users also can access existing Tweets containing hashtags, e.g., #radon, #radonawareness, #radonmitigation, and #lungcancer. Individual users' activities on the radon app, along with their Twitter handle, are saved on Triad Interactive Media's server. Through the app, users could order a free radon test kit at any time.

We conducted a pilot clinical trial using this app. Ninety six (96) undergraduates at the University of North Dakota in Grand Forks, ND (UND) were assigned to use the radon app for one month and were tested on several aspects of radon knowledge and testing using a pretest-posttest design.¹¹ We have recently published our findings.¹¹ We found that the use of the radon app: (1) significantly improved individuals' radon knowledge and generated positive attitudes toward radon testing; (2) significantly increased self-efficacy (i.e., an individual's perceived capability to order a radon test kit and use it); (3) significantly increased response efficacy (i.e., an individual's evaluation of the effectiveness of radon testing in preventing radon exposure); and (4) resulted in 24% of study participants ordering a free radon test kit. However, only a small percentage of participants actually used the test kit they obtained (i.e., employed the test in their home and returned it to the lab; a total test completion rate of 9%).

In summary, our pilot trial demonstrated that the radon app improved radon knowledge, motivation to test, and stimulated requests for free test kits. However, our pilot trial had a key limitation: there was no control group (i.e., a group not exposed to the app). Our present research builds and improves upon these preliminary findings. To do so, we will include a control group that receives usual care (radon information communicated via EPA brochures).

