6.2 FIDELITY

6.2.1 INTERVENTIONIST TRAINING AND TRACKING

Ideally, the fidelity of delivery would be monitored by measuring the amount of time persons in the experimental group spent time on the smartphone app. However, this functionality was not developed for financial reasons (the app developer required more money that we had to spend), nor was there any parallel for the comparison group, since there was no way to guarantee that they had indeed read the brochures we sent. However, we did verify the downloading of the app to the experimental group.

With regard to adherence, this was measured indirectly, via the percentage correct of tests of radon knowledge.

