9 STATISTICAL CONSIDERATIONS

9.1 STATISTICAL HYPOTHESES

- Primary Endpoint(s): **H₀**: The incidence of: (a) participants' requests for free radon kits and (b) participants utilizing the test kits and returned to Alpha Energy Labs among those assigned to the radon app condition and those assigned to the brochure condition will not differ. **H₁**: The incidence of: (a) participants' requests for free radon kits and (b) participants utilizing the test kits and returned to Alpha Energy Labs will be higher among those assigned to the radon app than the brochure condition.

H₀: The difference in the incidence of request for and utilization of radon test kits between the radon app and brochure conditions will not be affected by participants' gender, age, race, smoking status, or geographic location (state/county of birth). **H₁**: There is significant interaction between the radon app and brochure conditions and the variables above in terms of the proportion requesting and utilization of test kits.

- Secondary Endpoint(s): **H₀**: There will be no changes in radon knowledge among those assigned to the radon app condition and those assigned to the brochure condition. **H₁**: There will be more positive changes in radon knowledge among participants assigned to the radon app condition.

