9.4.7 SUB-GROUP ANALYSES

Primary endpoints will be analyzed based on gender, age, race, smoking status, or geographic location (state/county of birth):

H₀: The difference in the incidence of request for and utilization of radon test kits between the radon app and brochure conditions will not be affected by participants' gender, age, race, smoking status, or geographic location (state/county of birth). **H₁**: There is significant interaction between the radon app and brochure conditions and the variables above in terms of the proportion requesting and utilization of test kits. **Statistical test**: We will use multivariate regression analyses predicting incidence of requesting and utilization of test, while controlling for gender, age, race, smoking status, location, and time spent using the app with SAS. Interactions will be tested in multivariate models and significant interactions will be described by levels of univariate Z or chi-square tests.

Secondary endpoints will not be analyzed based on gender, age, race, smoking status, or geographic location (state/county of birth).

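### Ten unadjusted, unpowered interaction tests sit under the primary hypotheses, and at the pilot's 9% return rate the return models will often have no finite estimates

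*Combined protocol and SAP*

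**What the plan says.** Section 9.1 puts a second null/alternative pair under the primary endpoints. Its alternative is that "There is significant interaction between the radon app and brochure conditions and the variables above", the variables being gender, age, race, smoking status and state/county of birth. It covers both requesting and using a kit.

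Section 9.4.7 gives the method: "We will use multivariate regression analyses predicting incidence of requesting and utilization of test". The adjustment set of these models is given as "controlling for gender, age, race, smoking status, location, and time spent using the app". On the interactions themselves the section says: "Interactions will be tested in multivariate models and significant interactions will be described by levels of univariate Z or chi-square tests".

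Four other places bear on this:
- Section 2.2 reports that the one-month, app-only pilot of 96 students "resulted in 24% of study participants ordering a free radon test kit", and had "a total test completion rate of 9" percent.
- Section 9.2 sizes the trial at 100 or more per group, for a 20-point difference in proportions and odds ratios above three. It gives no interaction effect.
- Section 9.4.1 allows assumption checks and corrective procedures in general terms. No section states an alpha, a multiplicity rule, a coding for the modifiers or a method for sparse data. Section 9.4.9 (exploratory analyses) is marked not applicable.
- Section 6.2.1 says of measuring time on the app that "this functionality was not developed for financial reasons".

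**The concern.** A hypothesis listed with the primary endpoints is normally read as confirmatory. Here ten such tests have no error control and no power behind them, so a significant interaction would be weak evidence presented as a planned hypothesis test.

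Returned kits are also likely to be few. When one level of a modifier in one arm has no events, a logistic model with that interaction is separated: the maximum-likelihood estimate is infinite, and the software gives a warning or a meaningless coefficient. The analyst would then have to choose another method after seeing the data.

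The adjustment set also includes a covariate that the protocol says it had no means to collect.

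**Working it through.** **1. The plan's own figure.** Power for 20 points at 100 per arm, least favourable pair 40% v 60%, alpha 0.05 assumed. Pooled SE = √(2 × 0.25/100) = 0.0707; unpooled SE = √(2 × 0.24/100) = 0.0693.
- Two-sided: Φ[(0.20 − 1.96 × 0.0707)/0.0693] = 0.81.
- One-sided: Φ[(0.20 − 1.645 × 0.0707)/0.0693] = 0.89.

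This reproduces the stated 0.8 to 0.9, but for the main comparison only.

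**2. Number of tests and familywise error.** 5 modifiers × 2 outcomes = 10. If independent at 5%, 1 − 0.95^10 = 0.40. With state and county as separate terms there are 12, and 1 − 0.95^12 = 0.46. The tests are in fact correlated and some models are sparse. Simulation with no true interaction gave 0.36 to 0.50 with likelihood-ratio tests and 0.08 to 0.26 with Wald tests. The plan does not say which it would use.

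**3. Interaction power.** Ratio of odds ratios 3, 50/50 modifier, 50 people per cell. Var(log ratio) = Σ 1/[n p(1 − p)] over the four cells, with the odds in one app cell multiplied by 3.
- Returns, 9% in both arms: the raised cell has p = 0.229. Variance = 0.113 + 3 × 0.244 = 0.846, SE 0.920. Power = Φ(1.099/0.920 − 1.96) = 0.22.
- Returns, 9% v 4.5%: 0.16.
- Requests: 0.40 at 24% v 24%, 0.31 at 24% v 12%, 0.17 at 24% v 4%.
- If one level of the modifier holds only 10% of participants: 0.09 to 0.12 for returns and 0.09 to 0.19 for requests.

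**4. Expected returns.** App rate 9% (pilot); brochure rate 3% to 9% (assumed). 100 × 0.09 + 100 × 0.03 = 12; 100 × 0.09 + 100 × 0.09 = 18. With every modifier coded as one term and app time left out, the model has 7 parameters for main effects (with intercept and arm), 8 with one interaction and 12 with all five. Events per parameter are 12/8 = 1.5 to 18/8 = 2.3 with one interaction, and 12/12 = 1.0 to 18/12 = 1.5 with all five.

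**5. Separation.** Assumed shares: 15% non-white, 10% smokers, 45% born in state. Simulated trials of 100 per arm, several hundred per setting; ranges are across repeat runs.

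| Outcome, app v brochure | All five interactions | One at a time |
|---|---|---|
| Returns, 9% v 3% | 95–97% | 44–86% |
| Returns, 9% v 9% | 77–80% | 20–23% gender, age, location; 53% race; 64% smoking |
| Requests, 24% v 10% | 54–56% | 2–8% gender, age, location; 21–27% race; 41–44% smoking |

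Main effects alone separated in 40–45% of return models at 9% v 3%.

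**6. Check by hand.** With 10 smokers per arm, the chance that at least one arm has no event among its smokers is:
- Returns 9% v 9%: 1 − (1 − 0.91^10)² = 1 − 0.611² = 0.63.
- Returns 9% v 3%: 1 − (1 − 0.91^10)(1 − 0.97^10) = 1 − 0.611 × 0.263 = 0.84.
- Requests 24% v 10%: 1 − (1 − 0.76^10)(1 − 0.90^10) = 1 − 0.936 × 0.651 = 0.39.

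These agree closely with the simulated smoking figures (64%, up to 86%, and 41–44%). The 20–23% for gender, age and location at 9% v 9% comes mainly from the main effects. No smoker (20 in all) or no non-white participant (30 in all) has an event with probability 1 − (1 − 0.91^20)(1 − 0.91^30) = 1 − 0.848 × 0.941 = 0.20.

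**7. Sensitivity.**
- Returns at 18% v 9% (double the pilot's app rate): 67% separated with all five interactions, 53% with smoking alone.
- Requests at 24% v 10% with 200 per arm: 0% for gender, age and location, 6% for race and 11% for smoking.
- Coarser coding is the favourable case. With three location levels (smallest 15%) and 12% in the minority race category, 91% of return models with all five interactions separated at 9% v 9%.

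**The case against.** Several points against the concern are sound.

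- The 9% and 24% come from a one-month pilot without a control group. The protocol states no expected rate for either arm of this three-month trial, and returns could be higher. They could also be lower: if the 9% referred to those who ordered, the app arm would give about 24 × 0.09 = 2 returns.
- The 9% bears only on the five return tests. The request tests rest on 24%, and request models with one interaction usually fit.
- Section 9.4.7 does not say that all five interactions enter one model, so the 77–97% figures apply only to that reading. The category shares are assumed too, and 100 per arm is a minimum.
- The 40% and the separation rates do not simply add up. Wald tests become conservative under separation, so frequent separation goes with fewer false positives if Wald tests are used.
- Describing levels only after a significant interaction is stricter than routine subgroup testing. Objecting to that step is largely a matter of preference.
- Section 6.4 mentions back-end app data for adherence. It does not say that these include time, and section 6.2.1 says that function was not built.

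A reader might go further and infer that the return model cannot be fitted at all, that most of the ten tests will give false subgroup claims, or that the primary result is compromised. The documents support none of these. Separation is likely, not certain. The 40% is the chance of any false positive across ten tests. The primary analysis in section 9.4.2 is a separate Z test for proportions.

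What remains is the placement among the primary hypotheses, the absence of error control and interaction power, and the lack of any method for sparse data. The general wording on corrective procedures in section 9.4.1 names transformations and nonparametric tests as examples; neither deals with separation.

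**Conclusion.** The concern holds in a limited form. Ten interaction tests are listed with the primary hypotheses without multiplicity control, with power of about 0.16 to 0.40 even for a large interaction in an evenly split modifier. The chance of at least one false interaction is about 40% if the tests are independent and each is at 5%; the plan states no alpha, so that level is assumed.

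At the pilot's return rate, ordinary logistic return models will often have no finite estimates: roughly 80% to 95% of trials with all five interactions and 20% to 90% with one at a time. These figures rest on 100 per arm, brochure rates of 3% to 9% and the category shares above, none of which except the sample size is in the documents. For requests the problem is confined mainly to smoking and race when the brochure rate is low. Actual state or county categories would be sparser than the in-state split used here.

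Apart from sparsity, the model in section 9.4.7 cannot be run as written. It adjusts for time on the app, which section 6.2.1 says was not measurable. That variable also arises after randomisation and has no value in the brochure arm.

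**What to change.** - Section 9.1: move the interaction hypotheses out of the primary endpoint hypotheses and label them exploratory. List them in section 9.4.9 as well, or refer from there to section 9.4.7.
- Section 9.4.7, requests: test one modifier at a time, with coarse categories fixed in advance (for example, born in state v out of state). Use Firth-penalised logistic regression, which SAS offers. Report each interaction with a 95% CI and make no confirmatory claim.
- Section 9.4.7, returns: report counts by arm within each subgroup. Mark any penalised estimate as descriptive.
- Section 9.4.7, covariates: remove time on the app.

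The cost is a change of wording in the plan and somewhat less analysis. The downside is that no confirmatory interaction claim can be made, which this sample size could not support in any case. Keeping the tests confirmatory at 0.05/10 = 0.005 each would hold the familywise error at 1 − 0.995^10 = 0.049, but would lower the already low power and leave the separation unsolved.

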9.4.8 TABULATION OF INDIVIDUAL PARTICIPANT DATA

Individual participant data will be listed by measure and time point.

9.4.9 EXPLORATORY ANALYSES

N/A

10 SUPPORTING DOCUMENTATION AND OPERATIONAL CONSIDERATIONS

10.1 REGULATORY, ETHICAL, AND STUDY OVERSIGHT CONSIDERATIONS

10.1.1 INFORMED CONSENT PROCESS

10.1.1.1 CONSENT/ASSENT AND OTHER INFORMATIONAL DOCUMENTS PROVIDED TO PARTICIPANTS

Consent forms describing in detail the study intervention, study procedures, and risks will appear in the first page of the online survey questionnaire. Participants will be asked to read and proceed if they consent. The following consent material is submitted with this protocol: IRB-approved consent forms for pre-exposure and post-exposure surveys.

10.1.1.2 CONSENT PROCEDURES AND DOCUMENTATION

The consent form for pre-exposure survey and post-exposure surveys will appear at the very beginning of each online survey. COMM110 and 102 students who are interested in participating in this study will be asked to read the consent form by themselves. Completion and return of the online survey form implies that they have read the information in this form and consent to participate in the research. Since the research presents no more than minimal risk and includes no procedures for which written consent is normally required outside the research context, the IRB granted the waiver of signature requirement for informed consent.

10.1.2 STUDY DISCONTINUATION AND CLOSURE

This study may be temporarily suspended or prematurely terminated if there is sufficient reasonable cause. Written notification, documenting the reason for study suspension or termination, will be provided by the suspending or terminating party to study participants, investigator, funding agency, and regulatory authorities. If the study is prematurely terminated or suspended, the Principal Investigator (PI) will promptly inform study participants, the Institutional Review Board (IRB), and sponsor/funding agency and will provide the reason(s) for the termination or suspension. Study participants will be contacted, as applicable, and be informed of changes to study visit schedule.

Circumstances that may warrant termination or suspension include, but are not limited to:

- Determination of unexpected, significant, or unacceptable risk to participants
- Demonstration of efficacy that would warrant stopping
- Insufficient compliance of study staff to the protocol (i.e., significant protocol violations)
- Data that are not sufficiently complete and/or evaluable
- Determination that the primary endpoint has been met
- Determination of futility

The study may resume once concerns about safety, protocol compliance, and data quality are addressed, and satisfy the funding agency, sponsor, IRB, Food and Drug Administration (FDA), or other relevant regulatory or oversight bodies (OHRP, DSMB).

10.1.3 CONFIDENTIALITY AND PRIVACY

Participant confidentiality and privacy is strictly held in trust by the participating investigators, their staff, the safety and oversight monitor(s), and the sponsor(s) and funding agency. This confidentiality is extended to the data being collected as part of this study. Data that could be used to identify a specific study participant will be held in strict confidence within the research team. No personally-identifiable information from the study will be released to any unauthorized third party without prior written approval of the sponsor/funding agency.

All research activities will be conducted in as private a setting as possible.

The study monitor, other authorized representatives of the sponsor or funding agency, representatives of the Institutional Review Board (IRB), regulatory agencies or representatives from companies or organizations supplying the product, may inspect all documents and records required to be maintained by the investigator, including but not limited to, medical records (office, clinic, or hospital) and pharmacy records for the participants in this study. The clinical study site will permit access to such records.

The study participant's contact information will be securely stored at the clinical site for internal use during the study. At the end of the study, all records will continue to be kept in a secure location for as long a period as dictated by the reviewing IRB, Institutional policies, or sponsor/funding agency requirements.

Study participant research data, which is for purposes of statistical analysis and scientific reporting, will be transmitted to and stored in the PI's password-protected computer. This will not include the participant's contact or identifying information. Rather, individual participants and their research data will be identified by a unique study identification number. The study data entry and study management systems used by the study team will be secured and password protected. At the end of the study, all study databases will be de-identified and archived in the PI's password-protected computer.

Measures Taken to Ensure Confidentiality of Data Shared per the NIH Data Sharing Policies

It is NIH policy that the results and accomplishments of the activities that it funds should be made available to the public (see <https://grants.nih.gov/policy/sharing.htm>). The PI will ensure all mechanisms used to share data will include proper plans and safeguards for the protection of privacy, confidentiality, and security for data dissemination and reuse (e.g., all data will be thoroughly de-identified and will not be traceable to a specific study participant). Plans for archiving and long-term preservation of the data will be implemented, as appropriate.

Certificate of Confidentiality

To further protect the privacy of study participants, the Secretary, Health and Human Services (HHS), has issued a Certificate of Confidentiality (CoC) to all researchers engaged in biomedical, behavioral, clinical or other human subjects research funded wholly or in part by the federal government. Recipients of NIH funding for human subjects research are required to protect identifiable research information from forced disclosure per the terms of the NIH Policy (see <https://humansubjects.nih.gov/coc/index>). As set forth in 45 CFR Part 75.303(a) and NIHGPS Chapter 8.3, recipients conducting NIH-supported research covered by this Policy are required to establish and maintain effective internal controls (e.g., policies and procedures) that provide reasonable assurance that the award is managed in compliance with Federal statutes, regulations, and the terms and conditions of award. It is the NIH policy that investigators and others who have access to research records will not disclose identifying information except when the participant consents or in certain instances when federal, state, or local law or regulation requires disclosure. NIH expects investigators to inform research participants of the protections and the limits to protections provided by a Certificate issued by this Policy.

10.1.4 FUTURE USE OF STORED SPECIMENS AND DATA

Data collected for this study will be analyzed and stored in the PI's password-protected computer. After the study is completed, the de-identified, archived data will continue to be stored in the PI's password-protected computer, for use by other researchers including those outside of the study.

10.1.6 SAFETY OVERSIGHT

Safety oversight will be under the direction of the study team based on its self-assessments guided by sub-components of a Quality Management Plan (see Section 10.1.8).

10.1.7 CLINICAL MONITORING

N/A

10.1.8 QUALITY ASSURANCE AND QUALITY CONTROL

The clinical site will perform internal quality management of study conduct, data collection, documentation and completion.

Quality control (QC) procedures will be implemented as follows:

Informed consent --- Study staff will review both the documentation of the consenting process as well as a percentage of the completed consent documents. This review will evaluate compliance with GCP, accuracy, and completeness. Feedback will be provided to the study team to ensure proper consenting procedures are followed.

Source documents and the electronic data --- Data will be initially captured on source documents (see **Section 10.1.9, Data Handling and Record Keeping**) and will ultimately be entered into the study database. To ensure accuracy site staff will compare a representative sample of source data against the database, targeting key data points in that review.

Intervention Fidelity — Consistent delivery of the study interventions will be monitored throughout the intervention phase of the study. Procedures for ensuring fidelity of intervention delivery are described in **Section 6.2.1, Interventionist Training and Tracking**.

Protocol Deviations – The study team will review protocol deviations on an ongoing basis and will implement corrective actions when the quantity or nature of deviations are deemed to be at a level of concern.

Should independent monitoring become necessary, the PI will provide direct access to all trial related sites, source data/documents, and reports for the purpose of monitoring and auditing by the sponsor/funding agency, and inspection by local and regulatory authorities.

